11.4. Sample Storage and Disposal

All samples and associated results will be coded prior to being shipped from the site for analysis or storage to ensure confidentiality. After sample processing, samples (including but not limited to slides or DNA/RNA extracted) may be stored for a maximum of 15 years for the associated exploratory analysis with this study and indication following the completion of the study at Sponsor-designated central laboratories after which time they will be destroyed.

11.5. Analytical Procedures

Analysis will be conducted using adequately validated assays at Sponsor-designated laboratory(ies). The detailed analytical procedures will be described in the SOP at the assay laboratory(ies).

12. STATISTICAL CONSIDERATIONS

The statistical analysis methods will be documented in detail in the statistical analysis plan (SAP). The SAP will be finalized prior to database lock.

12.1. Timing of Analyses

The primary analyses for Phase 1 Dose Escalation (Part A) will be performed continuously until RP2D is identified.

The primary analysis for Phase 1 Dose Expansion (Part B) will be performed once all patients have completed the Safety Follow-up Period or at least 6 months have passed since the last patient was enrolled, whichever occurs first.

The primary analysis of the Phase 2 part (Part C) will be conducted when the majority of patients responding to TAS3351 have been observed for at least 6 months from their first onset of response.

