7.1.1. Efficacy Assessments

Efficacy assessments (including CT scan/MRI) will be performed by Investigator/local radiologist according to RECIST v1.1 guidelines at the timepoints outlined in the Schedule of Events (Section 1.3).

Radiological assessment must include MRI/CT of the chest, abdomen (and pelvis, if clinically indicated or obtained at baseline) at each time point, as well as assessment of all other known sites of disease. MRI of the brain should be performed if signs or symptoms suggestive of CNS metastases are present. The same method of assessment and the same technique must be used to characterize each identified and reported lesion at screening, throughout the study including the follow-up period. Contrast-enhanced CT scans or MRIs are the preferred methods for tumor assessments. If a contrast agent is contraindicated in a patient, obtain a non-contrast chest CT and enhanced MRI of the abdomen (and pelvis if clinically indicated). A CT should be performed using a ≤ 5 mm contiguous reconstruction algorithm.

For Part B and C of this study, all radiological imaging will be performed as indicated in the Site Imaging Manual provided by the central imaging core laboratory. Scans will be submitted to a Sponsor designated central imaging core laboratory for response assessment including RECIST v1.1, and/or exploratory analysis (eg, volumetric and viable tumor measurements). Detailed information regarding submission of images to the central imaging core laboratory is found in the Site Imaging Manual.

Note that complete response and partial response (PR) require confirmatory CT or MRI repeat assessment at least 4 weeks after the first detection of response. PET may be used to upgrade a response to a CR in a manner similar to a biopsy in cases where a residual radiographic abnormality is thought to represent fibrosis or scarring.²⁸

Patients who discontinue without documented radiographic disease progression per RECIST 1.1 should continue to undergo tumor assessments/scans according to the Schedule of Events until radiographic PD per RECIST v1.1 is documented, the study is completed, or consent is withdrawn.

7.1.2. 12-Lead Electrocardiogram

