12.3. Estimation of Sample Size

Part A:

Part A1: Phase 1 Dose Escalation

There will be up to 40 evaluable patients enrolled using the BOIN design, [REDACTED]. [REDACTED] Table 4 provides the dose-finding decisions given the numbers of patients treated at the current dose level, and the observed numbers of patients experiencing toxicity. A minimum of 3 patients at each dose level is required.

Part A2: Backfill patients

Approximately 20 patients will be added for “backfill” cohorts as needed in the Phase 1 Dose Escalation. The additional information from these “backfill” patients will broaden the amount of safety and preliminary anti-tumor activity data for TAS3351 at a potential active dose levels to inform the selection of the RP2D of TAS3351.

Part B: Phase 1 Dose Expansion

Approximately 40 patients (20 patients per cohort) will be enrolled in the Dose Expansion part of this study. Sample size considerations were based on estimating the proportion of responders with certain precision. If there will be 9 responders, a sample size of 20 patients per cohort would allow to exclude the current standard of care ORR of 25% (90% CI: 27.4%, 68.0%; see also Section 2.1.1)^{6,7,8,9} at 2-sided significance level of 10%.

Part C: Phase 2

Approximately 100 patients will be enrolled. Sample size considerations were based on estimating the proportion of responders with certain precision. The 95% exact CI for ORR would exclude the current standard of care ORR of 25%^{6,7,8,9} if the observed ORR is 35% or higher. If there are 35 confirmed responses, a sample size of 100 patients would allow to exclude the current standard of care ORR of 25% (95% CI: 25.7%, 45.2%) at 2-sided significance level of 5%. See Table 16.

Table 16: ORR 95%CI for Sample Size of 100 Patients

Observed ORR	Exact 95% CI
35%	(25.7%, 45.2%)
40%	(30.3%, 50.3%)
45%	(35.0%, 55.3%)

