12.5. Analysis Populations

The analysis populations in the study are defined in [Table 17](#).

Table 17: Definitions of Analysis Populations

Analysis Population	Definition
All Consenting Population	All patients who signed the ICF.
All Treated Population	All patients who received at least one dose of the study drug. This is the primary population for dosing, efficacy, and safety analyses.
DLT Evaluable Population	All patients in the Dose Escalation, except backfill patients, who either experienced a DLT during the 1st cycle of treatment including PK lead-in period, or who completed the 1st cycle without experiencing a DLT and with at least 80% of planned study treatments administered. This is the specific population for DLT summarization.
PK Analysis Population	All patients who received at least one dose of study drug and have at least one post-dose TAS3351 and/or TAS-05-14317 plasma concentration measurement will be evaluated for PK; unless significant protocol deviations may have affected the data or if key dosing information is missing. This is the primary population for PK analysis.
Pharmacodynamic/Biomarker Analysis Population	All patients in the All-Treated Population who have at least one evaluable baseline and one evaluable post-dose pharmacodynamic/biomarker data point for analyses.

Abbreviations: DLT=dose-limiting toxicity; ECG=electrocardiogram; PK=pharmacokinetic

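### The Part C analysis trigger sets no minimum follow-up for all treated patients, so it permits a cut-off date at which the primary ORR is understated

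*Protocol*

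**What the plan says.** Section 12.1 of the protocol times the Part C primary analysis by responders alone: it is to be "conducted when the majority of patients responding to TAS3351 have been observed for at least 6 months from their first onset of response". It gives no minimum follow-up for patients who have not responded, no interval after the last enrolment, and no statement that enrolment must be complete.

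Four other provisions bear on this:

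- **Denominator.** Efficacy is analysed on the All Treated Population (Table 17): "All patients who received at least one dose of the study drug". No minimum follow-up is attached.
- **Confirmation.** Under section 7.1.1, complete and partial responses "require confirmatory CT or MRI repeat assessment at least 4 weeks after the first detection of response". Table 2 schedules scans every 6 weeks from Cycle 1 Day 1, with a 7-day window either side.
- **Sizing.** Section 12.3 states: "Approximately 100 patients will be enrolled". It continues: "If there are 35 confirmed responses, a sample size of 100 patients would allow to exclude the current standard of care ORR of 25"%.
- **Part B.** Its analysis runs when all patients have completed Safety Follow-up or "at least 6 months have passed since the last patient was enrolled, whichever occurs first".

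The supplied SAP states in its introduction that it covers Parts A and B, so it adds nothing on the Part C cut-off.

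**The concern.** A treated patient enters the ORR denominator with the first dose but cannot enter the numerator until a second scan confirms the response. Early responders can satisfy the trigger while recent enrollees are still inside that gap. Those patients are then counted as non-responders because of when they joined, whatever the drug does for them.

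The estimate at stake is the Phase 2 primary endpoint, read against a 25% benchmark. The protocol's illustration sits on a sharp edge: 35 responses in 100 exclude 25%, and 34 do not. A few responses not yet confirmable at the cut-off could change how the result reads.

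**Working it through.** **1. The plan's own figures.** Clopper-Pearson 95% intervals for 100 patients reproduce Table 16: 35 responses give 25.7% to 45.2%, 40 give 30.3% to 50.3%, and 45 give 35.0% to 55.3%. For 34 responses the lower limit is 24.8%, so 35 is the smallest count that excludes 25%.

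**2. Earliest confirmation.** The first scan is at week 6. Adding 4 weeks gives week 10, or week 9 if the first scan is 7 days early (5 + 4). The next scheduled scan is week 12. With months of 30.4375 days, week 6 is 1.38 months, week 10 is 2.30 and week 12 is 2.76.

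**3. When the trigger is met.** Assumptions, none of them given in the documents: uniform accrual over A months, and all responses first seen at week 6. At time T, the share of responders seen so far with at least 6 months since onset is

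(T − 7.38) / min(T − 1.38, A), where 7.38 = 6 + 1.38.

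Setting this to one half gives T = A/2 + 7.38 for A up to 12 months, and T = 13.38 for longer accrual. I take the cut-off as T* = max(A, T), the earliest permitted date once the last patient is in. Two consequences follow:

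- T* falls before the last patient's week 12 once A/2 + 7.38 < A + 2.76, that is, A > 9.2 months. For week 10 it is A > 10.2 months.
- Above 13.4 months' accrual, the trigger has already been met when the last patient enrols. Read literally, it could be met with 13.38/18 = 74% or 13.38/24 = 56% of patients enrolled.

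**4. Patients affected.** The share with less than c months of follow-up is s = max(0, [A − (T* − c)]/A), with c = 2.30 or 2.76. For A = 12 and c = 2.76, this is (12 − 10.62)/12 = 11.5%. For A = 18, it is 2.76/18 = 15.3%.

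**5. Effect on ORR.** With a true ORR of 40%, the expected reading is 0.40 × (1 − s). The chance of at least 35 in 100 is the binomial tail at that rate; with s = 0 it is 0.87. Each range below runs between week-10 and week-12 confirmation.

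| Accrual (months) | T* (months) | Share affected | Expected ORR | P(at least 35/100) |
|---|---|---|---|---|
| 6 | 10.4 | 0% | 40% | 0.87 |
| 9 | 11.9 | 0% | 40% | 0.87 |
| 12 | 13.4 | 7.7-11.5% | 35.4-36.9% | 0.57-0.69 |
| 15 | 15.0 | 15.3-18.4% | 32.6-33.9% | 0.34-0.44 |
| 18 | 18.0 | 12.8-15.3% | 33.9-34.9% | 0.44-0.53 |
| 24 | 24.0 | 9.6-11.5% | 35.4-36.2% | 0.57-0.63 |
| 36 | 36.0 | 6.4-7.7% | 36.9-37.4% | 0.69-0.73 |

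**6. Simulation check.** I ran 4,000 trials of 100 patients per scenario, with week-12 confirmation for week-6 responses. Only confirmed responders counted towards the trigger, and onset was either all at week 6 or 70/20/10% at weeks 6, 12 and 18. At a true ORR of 40%, the chance of at least 35 responses was:

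- 6 months' accrual: 0.85-0.88
- 9 months: 0.71-0.75 (mean ORR 37.3-38.1%)
- 12 months: 0.30-0.34
- 15 months: 0.23-0.34
- 18 months: 0.31-0.41
- 24 months: 0.46-0.54
- 36 months: 0.63-0.66

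These values are mostly lower than the table for two reasons. Counting only confirmed responders lets the trigger be met sooner at 9 to 12 months' accrual, and later-onset responses need more time. With a 6-month minimum after the last enrolment (run for the mixed-onset pattern), mean ORR returned to 40% and the probability to about 0.87 at every accrual length.

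**The case against.** The strongest reply is that the rule permits an early cut-off but does not prescribe one. The protocol does not define the majority. It could mean a majority of the final responder set, which is known only after late enrollees have been scanned. The sponsor would bear the cost of cutting early and can wait. Accrual might also be quick enough for the problem to vanish, and section 12 defers detail to a SAP, so a Part C plan not supplied here could set a minimum. All of this stands as a limit on size. None of it puts a minimum into the stated rule.

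A reader might infer several stronger things that the documents do not support:

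- **That every patient enrolled within 12 weeks of the cut-off is a forced non-responder.** Section 7.1.1 asks for 4 weeks between scans, so confirmation is possible from about week 9 or 10.
- **That power for a planned test is lost.** Section 12.2 states no formal hypothesis and section 12.7.3.1 makes ORR descriptive. The count of 35 illustrates precision and is not a success rule. A downward bias cannot create a false claim of activity.
- **That Part B has an unconditional 6-month floor.** Part B runs at the earlier of two dates. The fair contrast is that either branch leaves each patient 6 months past enrolment or off treatment with Safety Follow-up complete. Part C has neither assurance.
- **That duration of response is mishandled.** Section 12.7.3.2 uses Kaplan-Meier, which censors responders with shorter follow-up. Asking for 6 months in a majority is a choice about data maturity.

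**Conclusion.** The point holds in a limited form. As written, section 12.1 allows the Part C ORR to be computed before late enrollees could have a confirmed response, and the supplied documents contain nothing that prevents it. The result would be an understated, conservative estimate, with no inflation of false-positive error.

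The size is conditional on assumed uniform accrual, on taking the earliest permitted cut-off after the last patient is in, and on when confirmation happens. Under the closed form with week-6 responses there is no effect at 6 to 9 months' accrual. The simulation shows a small loss at 9 months. From about 12 months the effect is material: roughly 3 to 7 percentage points at a true ORR of 40% across the closed-form scenarios, shrinking again as accrual lengthens towards 36 months. This is a gap in a stated rule that is cheap to close. It is not evidence that the analysis will be biased.

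**What to change.** Add to protocol section 12.1 that the Part C cut-off occurs only when both of the following hold, in addition to the existing majority-of-responders condition:

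- enrolment is complete; and
- every treated patient has had the opportunity for two post-baseline scans with confirmation, or has ended tumour assessments earlier.

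Allowing for the scan window, that means at least about 13 weeks after the last patient's first dose (week 12 plus 7 days). An interval of 18 weeks to 6 months would also capture responses first seen at later scans. The same sentence should define the majority: whether it refers to responders to date or after full enrolment, and whether their responses must be confirmed.

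The cost is one protocol sentence, and an analysis that may come about 3 to 6 months later than the earliest date now permitted.

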12.2. Statistical Hypothesis

No formal statistical hypothesis.

12.3. Estimation of Sample Size

Part A:

Part A1: Phase 1 Dose Escalation

There will be up to 40 evaluable patients enrolled using the BOIN design, [REDACTED]. [REDACTED] Table 4 provides the dose-finding decisions given the numbers of patients treated at the current dose level, and the observed numbers of patients experiencing toxicity. A minimum of 3 patients at each dose level is required.

Part A2: Backfill patients

Approximately 20 patients will be added for “backfill” cohorts as needed in the Phase 1 Dose Escalation. The additional information from these “backfill” patients will broaden the amount of safety and preliminary anti-tumor activity data for TAS3351 at a potential active dose levels to inform the selection of the RP2D of TAS3351.

Part B: Phase 1 Dose Expansion

Approximately 40 patients (20 patients per cohort) will be enrolled in the Dose Expansion part of this study. Sample size considerations were based on estimating the proportion of responders with certain precision. If there will be 9 responders, a sample size of 20 patients per cohort would allow to exclude the current standard of care ORR of 25% (90% CI: 27.4%, 68.0%; see also Section 2.1.1)^{6,7,8,9} at 2-sided significance level of 10%.

Part C: Phase 2

Approximately 100 patients will be enrolled. Sample size considerations were based on estimating the proportion of responders with certain precision. The 95% exact CI for ORR would exclude the current standard of care ORR of 25%^{6,7,8,9} if the observed ORR is 35% or higher. If there are 35 confirmed responses, a sample size of 100 patients would allow to exclude the current standard of care ORR of 25% (95% CI: 25.7%, 45.2%) at 2-sided significance level of 5%. See Table 16.

Table 16: ORR 95%CI for Sample Size of 100 Patients

Observed ORR	Exact 95% CI
35%	(25.7%, 45.2%)
40%	(30.3%, 50.3%)
45%	(35.0%, 55.3%)

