There will be up to 40 evaluable patients enrolled using the BOIN design, [REDACTED] Up to approximately 20 patients may be added for backfill cohorts as needed in the Phase 1 Dose Escalation (up to 60 patients total).

- Part B: Phase 1 Dose Expansion

Approximately 40 patients in 2 cohorts may be enrolled in the Phase 1 dose expansion in Part B of this study. Beside the RP2D, an additional lower dose level may be evaluated in the Phase 1 expansion. Sample size considerations for each cohort were based on estimating the proportion of responders with certain precision. If there are 9 responders, a sample size of 20 patients per cohort would allow to exclude the current standard of care ORR of 25% (90% CI: 27.4%, 68.0%).

- Part C: Phase 2

Approximately 100 patients will be enrolled in the Phase 2 part of this study. Sample size considerations were based on estimating the proportion of responders with certain precision. The 95% exact CI for ORR would exclude the current standard of care ORR of 25% if the overall ORR is 35% or higher. With 100 patients, if there are 35 responses, the 95% exact CI is (25.7 to 45.2%) to exclude the current standard of care ORR of 25%.

[figure not shown]
Efficacy Analysis

Descriptive statistics and summaries will be presented. Two-sided 95% CI will be estimated using the Clopper–Pearson method. For time to event endpoints, the Kaplan-Meier method will be used to estimate the median and percentile with the 2-sided 95% CI calculated using the Brookmeyer and Crowley method.

Safety Analysis

Safety data will be summarized descriptively.

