12.7.3. Efficacy Analyses

12.7.3.1. Primary Endpoint Analyses

Part A: Phase 1 Dose Escalation

Not applicable.

Parts B and C: Phase 1 Dose Expansion and Phase 2

ORR per RECIST v1.1 by ICR will be summarized descriptively. ORR will be estimated and the 2-sided 95% confidence interval (CI) will be calculated using the Clopper–Pearson method.

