3.3. Determination of Sample Size

Part A:

Part A1: Phase 1 Dose Escalation

There will be up to 40 evaluable patients enrolled using the BOIN (Bayesian optimal interval design) design, [REDACTED] A minimum of 3 patients at each dose level are required.

Part A2: Backfill patients

Approximately 20 patients will be added for “back-fill” cohorts as needed in the Phase 1 Dose Escalation. The additional information from these “back-fill” patients will broaden the amount of safety and preliminary anti-tumor activity data for TAS3351 at a potential active dose levels to inform the selection of the RP2D of TAS3351.

Part B: Phase 1 Dose Expansion

Approximately 40 patients (20 patients per cohort) will be enrolled in the Dose Expansion part of this study. Sample size considerations were based on estimating the proportion of responders with certain precision. If there will be 9 responders, a sample size of 20 patients per cohort would allow to exclude the current standard of care ORR of 25% (90% CI: 27.4%, 68.0%) at 2-sided significance level of 10%.

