5.5.1. Objective Response rate (ORR)

Primary Analysis in Part B – ORR by ICR

The following analyses will be performed.

The best overall response will be tabulated, and ORR with 95% CI will be calculated using the Clopper-Pearson method. Confirmed and unconfirmed responses will be listed.

- For Part B, 2-sided 90% CI will also be provided.
- Waterfall plot of target lesion will be provided.

Secondary Analysis in Part A, B – ORR by investigator

The following analyses will be performed.

- The best overall response will be tabulated, and ORR with 95% CI will be calculated using the Clopper-Pearson method.
- Waterfall plot of target lesion will be provided.

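### The Part B planning interval for 9 of 20 responders is misstated: the exact 90% CI is (25.9%, 65.3%), not (27.4%, 68.0%), and the protocol's analysis section omits the 90% interval that the sizing uses

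*Protocol*

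**What the plan says.** Protocol 12.3 plans Part B as follows: "Approximately 40 patients (20 patients per cohort) will be enrolled in the Dose Expansion part of this study". The size rests on precision, illustrated by one example in which nine patients respond: "a sample size of 20 patients per cohort would allow to exclude the current standard of care ORR of 25% (90% CI: 27.4%, 68.0" (per cent), at a two-sided 10% level. The synopsis prints the same interval, "90% CI: 27.4%, 68.0" (per cent). SAP 3.3 repeats it: "exclude the current standard of care ORR of 25% (90% CI: 27.4%, 68.0%) at 2-sided significance level of 10" (per cent).

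The analysis sections use different levels. For the primary endpoint of Parts B and C, protocol 12.7.3.1 says "ORR will be estimated and the 2-sided 95% confidence interval (CI) will be calculated" by the Clopper-Pearson method and names no other level. The efficacy paragraph of the synopsis also gives only 95%. SAP 5.5.1 plans the 95% Clopper-Pearson interval for Part B ORR by ICR and adds: "For Part B, 2-sided 90% CI will also be provided".

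**The concern.** An observed rate of 9/20 is 45%, and the printed interval looked too high and too wide for it at the 90% level. This example is the only quantitative support for 20 patients per cohort, so its figures should be right. A reader who takes the lower limit as 27.4% sees a comfortable distance from 25% and would expect the example to tolerate small changes in the number treated.

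The second question is whether the interval used to size Part B is one that the protocol plans to report. If only a 95% interval is reported, the reader cannot check the sizing statement against the result.

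**Working it through.** **Inputs.** x = 9 responders, n = 20 per cohort, reference rate 25%, two-sided level 10% (protocol 12.3, SAP 3.3). Analysis method: Clopper-Pearson (protocol 12.7.3.1, SAP 5.5.1).

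**Formula.** For x of n at two-sided level α:
- lower limit = the α/2 quantile of Beta(x, n − x + 1)
- upper limit = the 1 − α/2 quantile of Beta(x + 1, n − x)

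**Check on a figure the plan gets right.** Part C, 35/100 at 95%: lower from Beta(35, 66), upper from Beta(36, 65). The result is (25.7%, 45.2%), as printed in protocol 12.3 and Table 16. The formula therefore matches the plan's own exact intervals.

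**Part B.** For 9/20 at 90%: lower = 5% quantile of Beta(9, 12) = 25.87%; upper = 95% quantile of Beta(10, 11) = 65.31%. The printed (27.4%, 68.0%) is not reproduced.

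| Responders/n | Level | Lower | Upper | Excludes 25%? |
|---|---|---|---|---|
| 9/20 | 90% | 25.87% | 65.31% | yes |
| 9/19 | 90% | 27.39% | 67.99% | yes |
| 9/21 | 90% | 24.50% | 62.81% | no |
| 9/20 | 95% | 23.06% | 68.47% | no |
| 10/20 | 95% | 27.20% | 72.80% | yes |

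**Could another method explain the printed figure?** Ten other 90% methods were tried for 9/20:
- Wald (26.7, 63.3)
- Wald with continuity correction (24.2, 65.8)
- Wilson (28.4, 62.8)
- Wilson with continuity correction (26.3, 65.0)
- Agresti-Coull (28.4, 62.8)
- Jeffreys (28.0, 63.0)
- mid-P (27.6, 63.4)
- logit (28.1, 63.1)
- Blaker (27.0, 64.2)
- inverted exact test (27.5, 64.2)

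None has an upper limit above 65.8%, so none reaches 68.0%. A search of Clopper-Pearson intervals over all x/n with n from 10 to 44, at 80%, 90% and 95%, found one match: 9/19 at 90%.

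**Size of the error.** Lower limit: 27.4 − 25.9 = 1.5 points too high. Upper limit: 68.0 − 65.3 = 2.7 points too high. Margin over 25%: 27.4 − 25 = 2.4 points as printed; 25.9 − 25 = 0.9 points when corrected.

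**Cross-check by exact tail probability.** The lower limit exceeds 25% only if P(X ≥ x | n = 20, p = 0.25) is below α/2.
- P(X ≥ 9) = 0.0409: below 0.05, so the 90% CI excludes 25%; above 0.025, so the 95% CI does not.
- P(X ≥ 10) = 0.0139: below 0.025, so 10/20 excludes 25% at 95%.
- P(X ≥ 8) = 0.1018: above 0.05, so 9 is the smallest count out of 20 that excludes 25% at 90%.

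**The case against.** The strongest reply is that nothing planned depends on the misprint. Corrected, the 90% interval still excludes 25%, so the cohort size, the 9-responder example and the exclusion statement at the two-sided 10% level all stand. This is right, and it limits the point to a wrong figure and an overstated margin.

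A reader might go further and infer that a cohort with 9 responders would be declared a success under one document and a failure under the other. The documents do not support that:
- Protocol 12.2 states no formal hypothesis, and 12.7.3.1 makes the ORR summary descriptive.
- Protocol 4.2.2 rests the dose choice on the whole of the efficacy and safety data, and the proof of concept on Part B together with the backfill patients.
- Both documents size Part B on the 90% interval and both report a 95% interval. The SAP only adds the 90% one.
- No text claims that 9/20 excludes 25% at the 95% level. That level is tied to 25% only in Part C.

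It is also fair to say that the protocol leaves detailed methods to the SAP, and that SAP 5.5.1 supplies the matching interval. What remains is that the protocol's own analysis text lacks the interval on which its sizing paragraph relies, and that neither document says which of the two reported intervals the 25% reference belongs to.

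**Conclusion.** The printed Part B interval is wrong in three places across both documents. For 9/20 it should read (25.9%, 65.3%). The claim it supports remains true, but with a margin of 0.9 points instead of 2.4. That margin is fragile because the enrolment target is approximate and the analysis uses all treated patients: with 9/21 the 90% lower limit is 24.5% and 25% is no longer excluded. The 90%/95% mismatch is real but confined to the protocol: under the only interval that 12.7.3.1 plans, 9/20 does not exclude 25%, and 10/20 would be needed.

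The conclusion assumes that the planning interval was meant to be Clopper-Pearson. The sizing text does not name the method for Part B, but both analysis sections do, and the Part C figures reproduce with it. Without that assumption the printed pair is still unexplained, since no method tried gives it for 9/20. The match with 9/19 identifies the number, not how it came to be printed. The finding does not show that 20 per cohort is the wrong size, and it does not show a conflicting decision rule.

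**What to change.** 1. Replace (27.4%, 68.0%) with (25.9%, 65.3%) in the Part B sizing text of the protocol synopsis, protocol 12.3 and SAP 3.3.
2. In protocol 12.7.3.1, add the two-sided 90% Clopper-Pearson CI for Part B ORR alongside the 95% CI, to match SAP 5.5.1. Add one sentence saying that the 90% interval is the one to which the 25% reference in the sizing statement applies. The efficacy paragraph of the synopsis can carry the same addition.
3. Do not turn 9/20 into a formal threshold. Part B is descriptive, and the number treated may differ from 20.

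The cost is three number corrections and a sentence or two. No sample size, analysis or data collection changes. The only loss is that the planning example looks less comfortable than it does now.
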